## 9. Analysis Set and Population

### 9.1. Unblinding Procedure

The unblinding procedure was not described in protocol for study NN7999-3895 because an open-label design was used. Once all data discrepancies within the database are resolved with the clinical research units, the database is locked.

### 9.2. Analysis Set

#### 9.2.1. Full Analysis Set (FAS)

All main descriptions and analysis of efficacy will be based on the Full Analysis Set (FAS), as defined in ICH E9 guidelines. The FAS includes all patients exposed to N9-GP.

### 9.3. Sample Size and Analysis Population

*60 patients are planned to be screened and 40 patients are expected to complete the trial.*

For details, please see protocol Section 16.1.

### 9.4. Handling of missing data

No imputations will be performed in the event of missing data due to dropouts or omitted visits. All incomplete subject profiles will be retained in the analysis. In view of issues of reliability, all analyses will be conducted with completion failures removed.

## 10. Analysis Endpoints, Initial Assessment Definition, and Outcome Measures

### 10.1. Analysis Endpoints

The analysis endpoints are z-scores and change in z-scores for each neurocognitive assessment (see Table 2 for more details) against eTHINK population and US normative population (international normative population for  computerized tests), as well as responses on the Structural Development History and Hemophilia History.

### 10.2. Initial Assessment Definition

Initial Assessment data is the first assessment that has cognitive data for each subject. This first set of cognitive data may occur at different visits depending on the subject.

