5.3.3 Prophylaxis treatment

Regular prophylaxis must be initiated no later than 24 months of age or upon reaching 20 EDs whichever comes first, with a dose of 40 IU/kg N9-GP administered every 7th day (\pm 1 day).

If considered relevant, the investigator is permitted to prescribe administration of extra N9-GP bleeding preventive doses before demanding physical activities (e.g. sports). The next regular prophylaxis dose should not be postponed but be administered on the usual dosing day.

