8.3.3 Neurocognitive assessments

Neurocognitive assessments should be performed according to [Table 2-1](#), [Table 2-2](#), [Table 8-1](#) and [Table 8-2](#)

The following domains will be assessed in all countries:

- Executive function
- Attention/processing speed/working memory

Further, the following domains will be assessed in English speaking countries (e.g. Australia, Canada, United Kingdom, and the United States):

- Neurodevelopment or cognitive function and intelligence
- Emotional behaviour
- Adaptive behaviour

The timing of the neurocognitive assessments should be planned to allow as much flexibility for the patients as possible and can be made within ± 1 month of the assessment visits, except for the visit 1 and EOT visit where the neurocognitive assessments can be made at the visit date or up to 1 month ahead of the visit. The first assessment should be planned for the visit immediately after the patient turns either 1 or 2 years of age depending on country. Hereafter the visit schedule as found in [Table 8-1](#) and [Table 8-2](#) should be followed except if the next planned assessment visit is within three months of the initial assessment. All assessments should be performed using generally accepted standardised testing parameters to ensure optimal conditions for performance. A description of

Protocol
Trial ID: NN7999-3895
UTN: U1111-1135-9557
EudraCT No.: 2012-004867-38

~~CONFIDENTIAL~~

| | | |
|----------|------------------|---------------------|
| Date: | 05 November 2019 | Novo Nordisk |
| Version: | 8.0 | |
| Status: | Final | |
| Page: | 50 of 119 | |

neurocognitive assessments, training, equipment and related procedures will be provided in the Manual for neurocognitive assessments.

An independent External Expert Review Panel will evaluate the results of the neurocognitive assessments in context of the Structured Developmental History and Haemophilia History for each patient. Information regarding responsibilities, procedures, meeting frequency and workflow to be used by the External Expert Review Panel are specified in the External Expert Review Panel charter.

A CRO will provide the results from the External Expert Review Panel to Investigator as narrative reports including normalised domain scores and categorical assessment. It is the responsibility of the Investigator to report any findings if considered qualifying for an AE. If any findings are present at V0 it should be recorded as medical history.

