The following Structured Developmental History and Haemophilia History data will be collected in connection with the neurocognitive assessments:

- Demographics
- Parents/caregivers
- Brothers/sisters/other children
- Child's residence
- Pregnancy
- Birth
- Development
- Medical history
- Family health
- Educational history
- Haemophilia history

Protocol
Trial ID: NN7999-3895

UTN: U1111-1135-9557
EudraCT No.: 2012-004867-38

Date: 05 November 2019
Version: 8.0

Status: Final
Page: 51 of 119

Novo Nordisk

Table 8-1 Neurocognitive assessments by age for all countries

| Domain | Structured Developmental History and Haemophilia History | Executive Function | Attention / Processing Speed |
|---------------------------|---|------------------------------------|---|
| Assessment visits | The first assessment should be planned for the visit immediately after the patient turns 2 years of age. Hereafter the following visit schedule should be followed except if the visit is within 3 months from the initial assessment: Visit 1, visit 20, visit 23, visit 26, visit 28, visit 29, and all subsequent visits until and including EOT | | |
| Patient age (year:months) | | | |
| 1:0 to 1:11 | | | |
| 2:0 to 3:6 | Structured Developmental History and Haemophilia History | BRIEF-P (BRIEF-P 2:0-5:11y Parent) | |
| 3:7 to 3:11 | Structured Developmental History and Haemophilia History | BRIEF-P (BRIEF-P 2:0-5:11y Parent) | |
| 4:0 to 5:11 | Structured Developmental History and Haemophilia History | BRIEF-P (BRIEF-P 2:0-5:11y Parent) | ██████████ (Custom Battery - Peds (4-9)) |
| 6:0 to 6:11 | Structured Developmental History and Haemophilia History | BRIEF-2 (BRIEF2 5-18y Parent) | ██████████ (Custom Battery - Peds (4-9)) |
| 7:0 to 7:11 | Structured Developmental History and Haemophilia History | BRIEF-2 (BRIEF2 5-18y Parent) | ██████████ (Custom Battery - Peds (4-9)) |
| 8:0 to 9:11 | Structured Developmental History and Haemophilia History | BRIEF-2 (BRIEF2 5-18y Parent) | ██████████ (Custom Battery - Peds (4-9)) |
| 10:0 to 10:11 | Structured Developmental History and Haemophilia History | BRIEF-2 (BRIEF2 5-18y Parent) | ██████████ (Custom Battery - Adult (10-21)) |

Protocol
Trial ID: NN7999-3895UTN: U1111-1135-9557
EudraCT No.: 2012-004867-38Date: 05 November 2019
Version: 8.0Status:
Page:Final

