52 of 119 | **Novo Nordisk****Table 8-2 Additional neurocognitive assessments by age for English speaking countries (e.g. Australia, Canada, United Kingdom, and the United States)**

| Domain | Developmental History and Haemophilia History | Neurodevelopment / General Intelligence | Behavioural / Emotional | Adaptive behaviour |
|----------------------------------|--|---|--|----------------------------|
| Assessment visits | The first assessment should be planned for the visit immediately after the patient turns 1 year of age. Hereafter the following visit schedule should be followed except if the visit is within 3 months from the initial assessment: Visit 1, visit 23, visit 28, visit 30, visit 32, visit 34, ..., until and including EOT | | | |
| Patient age (year:months) | | | | |
| 1:0 to 1:11 | Structured Developmental History and Haemophilia History | Bayley-III | | ABAS-3 (0-5y Parent) |
| 2:0 to 3:6 | Structured Developmental History and Haemophilia History | Bayley-III | BASC3 (PRS-P Parent 2-5) | ABAS-3 (0-5y Parent) |
| 3:7 to 3:11 | Structured Developmental History and Haemophilia History | | BASC3 (PRS-P Parent 2-5) | ABAS-3 (0-5y Parent) |
| 4:0 to 5:11 | Structured Developmental History and Haemophilia History | WPPSI-IV | BASC3 (PRS-P Parent 2-5) | ABAS-3 (0-5y Parent) |
| 6:0 to 6:11 | Structured Developmental History and Haemophilia History | WPPSI-IV | BASC3 (PRS-C Parent 6-11) | ABAS-3 (5-21y Parent) |
| 7:0 to 7:11 | Structured Developmental History and Haemophilia History | WASI-II | BASC3 (PRS-C Parent 6-11 form) | ABAS-3 (5-21y Parent form) |
| 8:0 to 9:11 | Structured Developmental History and Haemophilia History | WASI-II | BASC3 (PRS-C Parent 6-11 form and SRP-C 8-11 patient form) | ABAS-3 (5-21y Parent form) |

Protocol
Trial ID: NN7999-3895

UTN: U1111-1135-9557
EudraCT No.: 2012-004867-38

Date: 05 November 2019
Version: 8.0

Status:
Page:

Final
53 of 119

Novo Nordisk

| | | | | |
|---------------|--|---------|--|----------------------------|
| 10:0 to 10:11 | Structured Developmental History and Haemophilia History | WASI-II | BASC3 (PRS-C Parent 6-11 form and SRP-C 8-11 patient form) | ABAS-3 (5-21y Parent form) |
|---------------|--|---------|--|----------------------------|

Protocol
 Trial ID: NN7999-3895
 UTN: U1111-1135-9557
 EudraCT No.: 2012-004867-38

~~CONFIDENTIAL~~

| | | |
|----------|------------------|---------------------|
| Date: | 05 November 2019 | Novo Nordisk |
| Version: | 8.0 | |
| Status: | Final | |

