### 8.2. Scheduled Visits

**Table 1: Visit Schedule for Neurocognitive Assessments**

Visit Number	Scheduled Interval	Analysis Visit
1, 20, 23, 26, 28-50	
 
BRIEF: Every 6 months (all countries)
 
██████ Battery: Every 6 months (all countries)
 
SDH: Every 6 months (all countries)
 
HH: Every 6 months (all countries)
 
Bayley-III / WPPSI-IV / WASI-II: Every 1 year (English-speaking countries only)
 
ABAS-3: Every 1 year (English-speaking countries only)
 
BASC: Every 1 year (English-speaking countries only)
 
	Yes
End of Trial		Yes
Unscheduled Visit		No

Study visits will be renamed such that the first visit is “Initial Assessment”, the next is “Assessment 2”, the following is “Assessment 3”, and so on, to account for the fact that not all subjects will be starting their neurocognitive assessments

at the same visit. If patients start on pre-prophylaxis and switch to prophylaxis at Visit 20, the assessments will be displayed under “Prophylaxis” in the tables.

The patient’s age when the Structured Developmental History (SDH) is completed will be used as the Visit Age for each visit.

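### For children first dosed before an instrument's minimum test age, change from Initial Assessment cannot show earlier neurocognitive loss, and SAP 12.2 pools it with change from pre-dose references

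*SAP*

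**What the plan says.** **Endpoint and reference.** SAP 10.1: "The analysis endpoints are z-scores and change in z-scores for each neurocognitive assessment". SAP 10.2 fixes the reference for change: "Initial Assessment data is the first assessment that has cognitive data for each subject". It adds: "This first set of cognitive data may occur at different visits depending on the subject". SAP 8.2 relabels the trial visits in sequence, "to account for the fact that not all subjects will be starting their neurocognitive assessments" at the same visit. SAP 12.2 then tabulates change from Initial Assessment for age-adjusted and haemophilia-adjusted z-scores. It makes no distinction by dosing status at the reference.

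**When testing starts.** Protocol 8.3.3: "The first assessment should be planned for the visit immediately after the patient turns either 1 or 2 years of age depending on country". For the all-country battery, Table 8-1 says: "The first assessment should be planned for the visit immediately after the patient turns 2 years of age". For the additional battery in English-speaking countries, Table 8-2 says: "The first assessment should be planned for the visit immediately after the patient turns 1 year of age". By instrument, the minimum age is 1 year for Bayley-III and ABAS-3, 2 years for BRIEF-P, and 4 years for the computerised tests (Table 8-1; SAP 10.4).

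**When dosing starts.** Protocol 5.3.3: "Regular prophylaxis must be initiated no later than 24 months of age or upon reaching 20 EDs whichever comes first". Sections 5.3 and 5.3.2 allow on-demand or slower pre-prophylaxis dosing before that point. Section 5.3 describes the usual switch to prophylaxis as falling between 1 and 2 years of age.

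**Outputs that do not use the child's own reference.** SAP 10.3 compares each result, initial and follow-up, with the eTHINK mean and SD. Level z-scores are tabulated under SAP 12.2. Protocol 16.5 plans a plot of each child's score against years of exposure.

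**The concern.** The neurocognitive tests are there because of a theoretical safety concern about PEG (Protocol 3.4). Change from a first score answers that question fully only if the first score precedes exposure. Here age triggers the first test and clinical need triggers the first dose, so the two are not aligned. A child already on treatment at his first test carries any earlier lasting loss into his reference, and subtraction removes it.

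Pooling then mixes two quantities: change since before treatment, and change since some point during treatment. A table of changes near zero could be read as no effect of N9-GP when part of it could not have shown one.

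**Working it through.** The plan states no power, error rate or effect size for these data, so there is no figure of its own to reproduce. One timeline input can be checked: 50 weekly doses take 50 weeks, which agrees with the minimum of 50 weeks for the main phase in Protocol 16.

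**1. Exposure before the reference.** Weeks = (minimum test age − age at first dose, in months) × 30.4375 / 7. On weekly dosing this is also roughly the number of EDs. On-demand or pre-prophylaxis dosing gives fewer EDs over the same time. The wait for the next visit adds up to about 12 weeks while visits are 10 ± 2 weeks apart.

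| Age at first dose | Weeks before test at 1 year | Weeks before test at 2 years | Weeks before test at 4 years |
|---|---|---|---|
| 6 months | 26 | 78 | 183 |
| 12 months | 0 | 52 | 157 |
| 18 months | 0 | 26 | 130 |
| 24 months | 0 | 0 | 104 |

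For example, (24 − 6) × 4.348 = 78 and (48 − 12) × 4.348 = 157.

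**2. Share of children with an on-treatment first assessment.** The documents give neither ages at first dose nor country mix. Assume age at first dose is uniform from 6 to U months, and a fraction e of children is in English-speaking countries. Assume also that everyone dosed at or after the test age is tested before dosing. Then share = (1 − e) × min(1, 18/(U − 6)) + e × 6/(U − 6).

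| U (months) | e = 0 | e = 0.5 | e = 1 |
|---|---|---|---|
| 24 | 100% | 67% | 33% |
| 36 | 60% | 40% | 20% |
| 72 | 27% | 18% | 9% |

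This is the share for a child's earliest instrument. For BRIEF-P, which starts at 2 years everywhere, the e = 0 column applies whatever the country mix. For the computerised tests the share is min(1, 42/(U − 6)): 100% for U = 24 or 36, and 42/66 = 64% for U = 72.

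**3. Effect on the change score.** Let L be a lasting loss, f the fraction of it that occurs before the reference, and s the share of children with an on-treatment reference. Expected change in such a child is L(1 − f). Expected pooled change is L(1 − s·f). Expected level z stays at L. Assume L = −0.5 SD, fully accrued by follow-up.

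- f = 0, 0.5, 1 gives a change of −0.50, −0.25, 0.00 in an on-treatment child.
- Pooled with f = 1: s = 9% gives −0.5 × 0.91 = −0.455; s = 100% gives 0.
- To link f to step 1, suppose the loss accrues evenly over the first two years of treatment and the test is at age 2. First dose at 6, 12 or 18 months then gives f = 1.5/2, 1/2 or 0.5/2, so 25%, 50% or 75% of the loss remains visible in change.

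**4. What the level scores still show.** With a normal score of SD 1, the chance of one result below −1 SD is 15.9% with no loss and 30.9% with a 0.5 SD loss, wherever the reference falls.

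**The case against.** The case against is substantial, and most of it limits the point without removing it.

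- **A reader might infer that most children are affected.** The documents do not say so. Entry is open to boys under 6 years (Protocol 6.2). Testing is scheduled at Visit 1, on the day or up to one month ahead (8.3.3), and clinical assessments preferably precede dosing (8.3). The 24-month limit governs regular prophylaxis only; a child first dosed at or after 24 months can have a pre-dose BRIEF-P. Section 5.3 makes early dosing plausible but gives no count. SAP version 1.0 is dated 22 April 2019, 57.7 months after first patient first visit. If testing began late the share would be higher, but the start date of testing is not stated.
- **A reader might infer that the whole neurocognitive evaluation hides early harm.** It does not. Findings are defined by level, at the Initial Assessment as well as later, and an expert panel reviews each child. These outputs keep the loss. Their limit is coarseness: SAP 10.3 calls a result within 1 SD normal variation, and also a visit with fewer than three results outside that limit. With a 0.5 SD loss, 69.1% of single scores stay above −1 SD.
- **Loss after the first test still shows in change.** This stands. The stated PEG concern is long-term exposure, so masking applies only to the part before the reference.
- **Exposure is already planned for display.** Protocol 16.5 does plan it. SAP 12.2, however, plots by visit, and SAP 8.2 has by then replaced visit numbers that track EDs with sequence labels. Its display under prophylaxis shows regimen, not exposure at the reference. The shells in SAP Appendix 1 are not in the text available, so the absence of a flag can be judged only from the SAP wording.
- **A single flag per child would misclassify.** Correct: a boy tested with Bayley-III at 12 months and dosed at 14 months has a pre-dose Bayley-III but an on-treatment BRIEF-P. The remedy has to work per instrument.

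**Conclusion.** The point holds for a defined group: children first dosed before the minimum test age of the instrument in question. For them, change from Initial Assessment cannot show a lasting loss that came earlier, and pooling biases the tabulated change toward no harm. The bias in the pooled mean is |L|·s·f. With L = −0.5 SD it lies between 0 and 0.5 SD, depending on the affected share and on how much of the loss came first. The effect size, its timing and the age distributions are assumptions; none comes from the documents. Neither a majority of children nor the neurocognitive evaluation as a whole can be called affected on this evidence. The output is descriptive with no decision rule attached, so this is a cheap improvement, but one that alters what the change table can support.

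**What to change.** - **SAP 10.2:** define the reference per instrument. Flag it as pre-dose (on or before the first N9-GP dose) or on-treatment. Record EDs and time since first dose at that assessment.
- **SAP 12.2, tables:** tabulate change from Initial Assessment separately for the two groups.
- **SAP 12.2, figures:** plot individual scores against time of exposure, as Protocol 16.5 states.
- **Interpretation:** state that for on-treatment references any conclusion about early harm rests on the norm-referenced level z-scores, not on change.

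The cost is SAP wording and a few derived variables from dosing and assessment dates already collected. SAP section 6 permits revision before database lock. No visit, test or treatment changes. The downside is small, imprecise cells: with about 40 expected completers divided by instrument and age form, the pre-dose groups may be too small for more than a listing. Showing that is still more informative than one pooled mean of two different quantities.

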### 10.3. Definition of Findings – Initial and Follow-Up

Based on the results from the eTHINK trial (all age groups pooled) the mean and standard deviation (SD) will be calculated for composite scores of all tests (see Table 2 for primary outcome measures). Each patient's individual results from each test (initial and follow-up assessments) from this trial will be compared to the mean and SD from the respective test from the eTHINK trial. If the patient's results are greater than 1 SD above the eTHINK mean (or less than -1 SD below the eTHINK mean), this will be treated as potential increase (or decrease) of the respective neurocognitive function and will be discussed with experts at the external expert review panel (EERP). If the absolute value of change from the eTHINK mean is  $\leq 1$  SD, the change will be categorized as "normal variation" rather than signal. If less than three different test results from the same visit are outside the defined threshold of 1 SD, the result will also be categorized as "normal variation", but still discussed with experts during the EERP.

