### **Custom Battery (DET, IDN, ONB; Attention/Processing Speed)**

Clinical assessment of attention usually depends on three sources of information: (1) psychometric tests designed to measure other cognitive functions, (2) specific neuropsychological tests of attention; and direct behavioral observation and measurement. Assessment often requires the clinician to obtain information about performance under different conditions. Measures of attention include attention span, divided attention, switching, response intention and planning, sustained performance and vigilance, and information-processing speed.

Information processing speed along with working memory have been identified as measures of cognitive impairment. While traditionally clinicians assessed with the Paced Auditory Serial Addition Test (PASAT), over the past decade the advent of computerized tests of information processing have been relied on to assess processing speed. The [REDACTED] computerized cognitive test battery proposed for this study includes an assessment of processing speed, attention/vigilance, and working memory.

- [REDACTED] Custom Battery (Peds platform, ages 4-9; Adult platform, ages 10-21)
  - Detection test (processing speed, psychomotor function)
  - Identification test (attention/vigilance)
  - One Back Test (working memory)

*Note: Ages 4-5 years old will be administered with pediatric Detection and Identification. Ages 6-9 years old will be administered with pediatric Detection, Identification, and One Back. Ages 10-21 will be administered with adult Detection, Identification, and One Back.*

Although each of the [REDACTED] computerized cognitive tests yields multiple outcome measures, research by [REDACTED] has identified a set of measures that are optimal for the detection of cognitive change in clinical trials at both the group and individual level (Falleti et al., 2006; Maruff et al., 2009; Bland & Altman, 1996a; Bland & Altman, 1996b).

For each [REDACTED] computerized cognitive test, a single primary outcome measure was selected prior to data analysis from each test in the battery to minimize experiment-wise error rates. Each primary outcome measure was selected because it has been shown to be optimal for the detection of change because:

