### 10.5. Other Outcome Measures

The following composite scores will be computed and analyzed:

- Attention Domain Composite
  - o Peds Age 4-5: DET, IDN speed scores must exist
  - o Peds Age 6-9: DET, IDN, ONB speed scores; at least two of three scores must exist
  - o Ages 10-21: DET, IDN, ONB speed scores; at least two of three scores must exist

The composite scores will be calculated by:

- 1) Standardizing each of the test scores included in the cognitive domains against age-matched US normative population (international normative population for [redacted] computerized tests) data for that test (Section 10.6.1 specifies the procedure for the standardization of the tests for the purposes of creating the Attention Domain Composite score).
- 2) Computing the average of the available standardized test scores if the required number of scores available is met (as described above).

The Attention Domain Composite score is normalized based on age and therefore serves as the age-adjusted z-score in summary tables without any further calculations.

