#### 11.1. Computerized Test Completion Criteria

For each of the computerized tests, subjects must provide sufficient responses to allow computation of reliable performance measures. For the majority of computerized tests, the term “sufficient” has been defined as a Test Completion criterion. The number of trials required for Test Completion is unique to each test. They do not vary for different patient groups or study samples.

The completion criteria set forth a priori for each test were as follows:

- DET: The number of responses provided by the subject is  $\geq 100\%$  of the desired number of trials (responses  $\geq 35$ )
- IDN: The number of responses provided by the subject is  $\geq 100\%$  of the desired number of trials (responses  $\geq 30$ )
- ONB: The number of responses provided by the subject is  $\geq 100\%$  of the desired number of trials (responses  $\geq 31$ )

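### SAP 10.3 labels an increase or decrease of function from distance to the eTHINK mean at one visit, with no within-child criterion and with high and low results counted together; 10.2 sets one baseline per child, not per instrument

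*SAP*

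**What the plan says.** SAP 10.3 takes the mean and SD from eTHINK, all ages pooled; these "will be calculated for composite scores of all tests (see Table 2 for primary outcome measures"). Every result in this trial, initial or follow-up, is set against them. For a result more than 1 SD above or below the eTHINK mean, "this will be treated as potential increase (or decrease) of the respective neurocognitive function", and it goes to the external expert review panel. A result within 1 SD is normal variation.

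A second condition works at visit level: "If less than three different test results from the same visit are outside the defined threshold of 1 SD", the result is also called normal variation, though the panel still discusses it. No direction is attached to this count.

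SAP 10.2 defines the baseline: "Initial Assessment data is the first assessment that has cognitive data for each subject". SAP 10.1 makes change part of the endpoint: "The analysis endpoints are z-scores and change in z-scores for each neurocognitive assessment". SAP 12.1 and 12.2 tabulate and list change from the prior and from the Initial Assessment, plot scores per patient, and orient every z-score so that positive is better. None of these sections gives a cut-off for change.

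**The concern.** The neurocognitive tests are there because the protocol (3.4) names a theoretical concern about long-term PEG exposure. In a single-arm trial, harm that develops on treatment would show mainly as a decline in the child's own scores. The only definition of a finding in these documents uses words of change but measures level, and it applies even at the initial assessment, where no change can have been observed. So it can label a stable child and pass over a falling one. Because improvements count towards the same minimum of three, many typical children reach it. With one Initial Assessment per subject, some change scores have no baseline on the same instrument.

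**Working it through.** **The rule applied to fixed cases.**
- +0.9 SD falling to −0.9 SD on every score: inside ±1 both times, so normal variation at both visits, despite a fall of 1.8 SD.
- Stable at −1.1 SD on three scores: meets the decrease label at every visit.

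**Scores per visit (k)**, from SAP Table 2 primary measures and Protocol Tables 8-1 and 8-2:
- Ages 2:0–3:11, non-English-speaking countries: BRIEF-P 4, so k = 4.
- Ages 4:0–5:11, same countries: BRIEF-P 4 + computerised battery 3, so k = 7.
- Ages 4:0–5:11, full English-language visit: 7 + WPPSI-IV 2 + BASC-3 parent 3 + ABAS-3 4, so k = 16.

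**Assumptions (not in the documents).** Scores are standard normal on the eTHINK scale, with equal inter-score correlation 0.3, 0.5 or 0.7 and retest correlation r = 0.7 or 0.8. A score is a true level (variance r) plus visit noise (variance 1 − r). Results are simulated and good to about one percentage point. The plan states no error rate for the rule, so there is none to reproduce.

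**Chance of meeting the minimum at one visit, no effect.** For one score P(|Z| > 1) = 0.317, and 0.159 in the adverse direction alone.

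| k | 3 or more outside ±1 | 3 or more below −1 |
|---|---|---|
| 4 | 12–20% | 5–10% |
| 7 | 36–38% | 15–18% |
| 16 | 62–87% | 30–39% |

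Some primary scores are built from others; the Attention Domain Composite, for instance, comes from "Computing the average of the available standardized test scores if the required number of scores available is met". Modelling global and composite scores as averages of their parts changes the two-directional figures to 19–26%, 37–40% and 57–80%, so the conclusion does not turn on this.

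**Detection of a 1.5 SD fall on all scores, k = 4, by starting level.** Visit noise has SD √(1 − r) = 0.548 or 0.447. From +0.9 the new level is −0.6, so one score falls below −1 with probability Φ(−0.4/0.548) = 0.23 or Φ(−0.4/0.447) = 0.19, and three of four must do so.
- Start +0.9 SD: 6–16% labelled
- Start +0.5 SD: 37–43%
- Start at the mean: 80–88%

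**The same fall averaged over eTHINK-like children.** The alternative rule counts three or more results below −1, or three or more that fell by over 1.5 SD from the child's first score.

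| k | Present label | Alternative rule |
|---|---|---|
| 4 | 64–65% | 72–75% |
| 7 | 79–89% | 87–94% |
| 16 | 90–99% | 94–100% |

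**Unchanged child labelled at least once in follow-up.** A two-year age band is about 104 weeks. At 24-week spacing that allows four follow-ups (104/24 = 4.3). The English-language tests are yearly, which allows two.

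| k (follow-ups) | Present label | Alternative rule |
|---|---|---|
| 4 (four) | 28–43% | 11–23% |
| 7 (four) | 64–74% | 29–39% |
| 16 (two) | 78–97% | 40–54% |

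The change flag adds little because change has SD √(2(1 − r)) = 0.775 or 0.632. An unchanged score then falls by more than 1.5 with probability Φ(−1.94) = 0.026 or Φ(−2.37) = 0.009.

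**Baseline.** A child in an English-speaking country first assessed at age 1 has Bayley-III and ABAS-3 at that visit. WPPSI-IV and the computerised battery start at 4:0, and BRIEF2 replaces BRIEF-P at 6:0. Read literally, 10.2 leaves these later instruments without a same-instrument Initial Assessment. Change from prior remains available once an instrument has been given twice.

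**The case against.** The strongest reply is that the label decides little. Results below the minimum of three are still discussed. Under Protocol 8.3.3 the independent panel evaluates the results together with each child's developmental and haemophilia history, and the investigator decides whether a finding is an adverse event. A fall from +0.9 to −0.9 SD would be visible in the patient plots and the change listings. The panel works to a charter that is not in these documents and may hold its own decline rule. Comparing level with eTHINK is also what Protocol sections 16 and 16.5 ask for, and counting both directions over-includes rather than hides. All of this stands. It limits the consequence but does not make the 10.3 category correct.

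Two stronger readings are tempting. One is that declines would go unseen in this trial; the planned change tables, plots and panel review do not support that. The other is that the minimum of three cannot be reached at some visits. The SAP does use the word test for single parts of the battery ("a single primary outcome measure was selected prior to data analysis from each test in the battery"; "The completion criteria set forth a priori for each test were as follows"), and counted that way a BRIEF-P-only visit offers one result. But 10.3 points to the Table 2 primary measures, which give at least four, so this is a matter for clarification.

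On 10.2, a per-instrument baseline may be intended: 12.2 lists change on each instrument, and the example tables in Appendix 1 are not in the text available here.

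**Conclusion.** The point holds as one to consider. As written, 10.3 treats a single-visit level as a potential change, has no within-child criterion although change is an endpoint, and lets improvements count towards the minimum. SAP 10.2 does not state a baseline for instruments introduced later. These are findings of text and need no simulation.

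The size rests on the assumed correlations and on counting Table 2 primary scores. With 16 scores the main cost is labels on typical children. With four it is missed falls in children who start above the eTHINK mean. The average gain in detection from the alternative rule is modest, about 8 to 10 points at k = 4 and less at k = 16. The larger gain is fewer labels on unchanged children. Whether the trial as a whole lacks a decline criterion cannot be settled without the panel charter; only its absence from 10.3 can.

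**What to change.** - **10.3, direction:** count only adverse-direction results towards a safety signal and list improvements separately.
- **10.3, change:** keep the level criterion, because harm before the first assessment at age 1 or 2 shows only in level. Add a within-child decrease flag against the first score on the same instrument and form, with its threshold fixed before database lock (for example 1.5 SD). If the charter already has such a rule, cite it instead.
- **10.2:** define the Initial Assessment per instrument and age form.
- **Clarification only:** state in 10.3 that the three results are Table 2 primary scores.

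The cost is SAP wording and minor programming, with no new assessments; the SAP introduction allows version-controlled revision before database lock. Over the follow-ups considered, a 1.5 SD flag adds at most about 3 points of false labels to the adverse-only count at k = 4 or 7, and about 4 at k = 16. The total stays well below that of the present label. Two limits remain: there is no change flag at the first visit on a new form, and slow drift across forms shows only through the level criterion.
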